2.5 Rationale for the OMWaNA study

Globally, there are 2.6 million neonatal deaths each year, and most of these deaths occur in small neonates before stabilisation. The OMWaNA trial aims to assess the effectiveness of KMC in reducing mortality in a population where the benefits of KMC are currently uncertain, a finding that would have important implications for global health policies. The OMWaNA trial is innovative in that it will allow us to determine the effect of KMC initiated before stabilisation on neonatal mortality within 7 days. By comparing the incremental cost and cost-effectiveness of KMC relative to standard care, this trial will be the first to assess the value for money of KMC. These findings will be crucial to help ensure the sustainability of this intervention. In addition, as part of the wider study we will use data from the trial to explore the physiological mechanisms by which KMC may reduce mortality, which have been poorly researched to date.

3. Study Setting and Design

3.1 Study Setting

The host institution for the trial will be the MRC/UVRI and LSHTM Uganda Research Unit in Entebbe. The trial will be undertaken in collaboration with Makerere University and LSHTM. These institutions are internationally recognised centres of excellence for research, with significant experience conducting and monitoring RCTs.

The study will be conducted in five sites in Uganda:

- Jinja Regional Referral Hospital (JH)
- Masaka Regional Referral Hospital (MH)
- Entebbe Regional Referral Hospital (EH)
- Iganga District Hospital (IH)
- Kawempe National Referral Hospital (KNRH)

JH, EH, and IH each provide care to ~5,000 to 6,000 neonates per year. MH provides care to ~10,000 neonates per year, and KNRH provides care to ~8,000 neonates per year. Current practice at these sites is to provide KMC for stable neonates $\leq 2000\text{g}$, according to WHO guidelines. MH, EH, and KNRH have research linkages with MRC/UVRI, and JH and IH have linkages with Makerere. Makerere has established health surveillance systems in the Busoga region where JH/IH are located.

3.2 Design of the Trial

This is a four-centre, individually randomised, controlled, superiority trial with two parallel groups; an intervention arm allocated to receive KMC and a control arm allocated to receive 'standard' care.

3.2.1 Randomisation

Treatment allocation will be random and in a 1:1 ratio between groups. The random allocation sequence will be computer generated centrally at LSHTM stratified by birthweight (<1000, 1000-1499, or ≥ 1500 g) and recruitment site. Birthweight is an important predictor of newborn survival. Neonatal mortality is 2-fold higher in SGA term neonates and 15-fold higher in SGA preterm neonates compared to appropriately sized term neonates (16). At each site, a laptop will be programmed with the random allocation sequence. This will be done in RedCap to avoid any possibility of viewing the allocation sequence. Allocation will only be revealed after the study medical officer at the site has completed entry of the mother's and neonate's details and all required screening data (see Section 5.3) into RedCap. The entry details will then be transferred to MRC/UVRI. Each site will have one spare laptop in case of breakdown or theft; if both fail, the site will revert to random allocation using telephone as the back-up option.

3.2.2 Blinding

Given the nature of the KMC intervention, blinding parents/caregivers is not possible. Process and outcome data will be anonymised, and all analyses will be blinded.

3.2.3 Details of the Intervention arm

Neonates randomised to the intervention group will receive KMC along with conventional therapies (e.g., IV fluids, antibiotics, oxygen) delivered according to standardised clinical guidelines (see Section 3.2.5). Parents will be encouraged to provide KMC as close to continuously as possible. While we anticipate the mother will be the primary KMC provider, a family member or close friend (helper) may also provide KMC. For interruptions due to mothers carrying out activities like bathing and going to the rest room, a family member or helper will be encouraged to take over KMC while the mother is away. If the mother has no family member or helper to continue KMC, the baby will be placed into an incubator or radiant heater according to standard care until the mother or another family member returns.

KMC will continue to be encouraged until discharge and at home after discharge, as per WHO guidelines (commonly practised until the baby is 2500g or around their due date or resists the KMC position, and this is often for 4 to 10 weeks).

3.2.4 Details of the Control arm

Infants randomised to the control group will receive standard neonatal care for that centre. Incubators and radiant heaters are the standard mode of thermal support for small and preterm neonates. It is common practice for several babies to share a single incubator. Conventional therapies will be administered according to standardised guidelines, as in the intervention arm. These include IV fluids (given by bolus or burette), respiratory support with nasal cannula oxygen and CPAP, first line IV antibiotics (ampicillin and gentamicin), and first line anti-seizure medications (phenobarbital). Feeding support in small and preterm infants is typically via nasogastric tube, spoon, syringe or cup. Infants in the control group can transition to routine (intermittent) KMC once stable (see Section 3.2.5), in line with study site standard clinical procedures.

3.2.5 Clinical Stability Criteria

Neonates will be considered stable when the following criteria have been met for a continuous period of at least 24h [criteria consistent with the WHO I-KMC trial (61)]:

- (i) Breathing spontaneously with $\text{SpO}_2 >90\%$ in room air
- (ii) No need for supplemental oxygen or CPAP
- (iii) Respiratory rate 40 to <60 breaths per minute
- (iv) No apnoea
- (v) HR 80 to <180 beats per minute
- (vi) Axillary temperature 36.0 to 37.4 degrees Celsius
- (vii) No need for IV fluids

3.2.6 Concomitant Therapies and Medications

All enrolled neonates will receive clinically indicated treatments, including but not limited to oxygen, IV fluids, antibiotics, aminophylline, anticonvulsant medicines, and phototherapy. Standardised clinical guidelines will be followed for common neonatal conditions, including preterm fluids/feeding (including breastfeeding), presumed and proven sepsis, respiratory distress, jaundice, and seizures. Bubble CPAP will be provided at the discretion of the on-duty paediatrician, if this is local standard of care. Jaundice will be treated with phototherapy for neonates in both arms. All caregivers will be trained in KMC regardless of study arm.

3.3 Design of the Economic Evaluation

The incremental cost, cost-effectiveness, budget impact, and equity of KMC for neonates before stabilisation relative to standard care, from the societal perspective (provider and household combined) will be examined, along with the effects of the intervention on both the health of babies (measured in disability-adjusted life-years, DALYs) and the wellbeing of the mothers and babies in the study. The economic evaluation will respond to decision makers' key policy questions regarding KMC and adhere to the principles, methodological specifications, and reporting standards of the latest reference cases for economic evaluations (62,63). Both financial costs – actual monies paid – and economic costs – the full value of all resources used – will be assessed. We will consider cost variation (e.g., between hospitals) and how costs may differ outside the trial setting.

We will utilise the Women's Capabilities Index (WCI) to assess women's well-being (13). The WCI is a multidimensional measure based on Sen's capability framework for assessing women's quality of life. Originally developed in Malawi, the WCI is now being adapted and tested for use in Uganda. It is an innovative composite measure of quality of life that will allow the broader benefits to the mother of practising KMC compared to standard care to be captured.

3.4 Design of the Process Evaluation

The process evaluation will explore causal pathways for the clinical effects of KMC initiated before stabilisation relative to standard care (Objective 2) and examine barriers and facilitators to initiating KMC before stabilisation to inform uptake and sustainability in Uganda (Objective 3). This evaluation

will consider both intended (beneficial) and unintended (negative) clinical effects, assessing how and why effects were attained and what systems changes will be required by whom as a result. The process evaluation will include focus group discussions (FGD) with neonatal healthcare providers, parents (intervention and control arms), and hospital administrators after 6 and 18 months of recruitment. In-depth interviews (IDI) with mothers will explore social and cultural factors that may influence maternal coping and compliance with care recommendations. IDIs with parents whose babies died during the hospital stay, including those who experienced a death in the KMC position, will explore parental experiences of trauma and bereavement. The process evaluation will include four phases (64):

- 1) Design
- 2) Pilot
- 3) Evaluation
- 4) Formation of recommendations to improve uptake (if intervention is found to be beneficial)

The process evaluation will be designed with stakeholder inputs, conducting two half-day workshops prior to the start of the trial at MRC/UVRI in Entebbe. The first workshop will include district health authorities, local community leaders, paediatricians, newborn nurses, and parents. The second will include local academics (MRC/UVRI, Makerere University), professional health organisations (Uganda Paediatric Association), and national (Ministry of Health) and international (UNICEF, International KMC Network) policy-makers.

4. Selection and Withdrawal of Participants

4.1 Participants

The trial will include neonates born weighing $\geq 700\text{g}$ and $\leq 2000\text{g}$, aged >1 and <48 hours, and for whom the indication for KMC is “uncertain” according to WHO guidelines concerning clinical stability (3). The process and economic evaluations (Objectives 2-4) will include administrators, providers, and parents of neonates at the four hospitals.

4.2 Eligibility Criteria for the Trial

Participants must meet the following inclusion criteria and not have any of the exclusion critieria to be able to participate in the trial.

4.2.1 *Inclusion criteria*

- Neonate admitted to JH, MH, EH, IH, or KNRH (inborn or outborn)
- Singleton, twin, or triplet (if triplet pregnancy resulted in demise/stillbirth of one or more fetuses)
- Birthweight $\geq 700\text{g}$ and $\leq 2000\text{g}$
- Chronological age 1-48 hours at time of screening
- Alive at time of recruitment
- Parent/caregiver able and willing to provide KMC
- Parent/caregiver willing to attend follow-up visit
- Indication for KMC “uncertain” according to WHO guideline concerning clinical stability: pragmatically defined as receiving ≥ 1 therapy: oxygen, CPAP, IV fluids, therapeutic antibiotics, phenobarbital

4.2.2 Exclusion criteria

- Result of multifetal pregnancy (triplets and above, unless triplet pregnancy resulted in demise/stillbirth of one or more fetuses)
- Indication for KMC “certain” according to WHO guidelines: pragmatically defined as clinically well neonates receiving none of the above therapy-based criteria
- Severely life-threatening instability defined as $\text{SpO}_2 < 88\%$ in oxygen AND ≥ 1 of:
 - Respiratory rate < 20 or > 100 breaths/min
 - Apnoea requiring bag-mask ventilation
 - HR < 100 or > 200 bpm
- Severe jaundice requiring immediate management
- Active neonatal seizures
- Major congenital malformation
- Parent does not provide written informed consent to participate in trial (Appendix A)

4.3 Eligibility Criteria for Focus Group Discussions and Interviews

Participants must meet the following inclusion and exclusion criteria to participate in FGDs and interviews.

4.3.1 Inclusion criteria

- Key stakeholder (parent of hospitalised neonate, neonatal healthcare provider (nurse or doctor), hospital administrator) at JH, MH, EH, IH, or KNRH
- Policy makers (WHO, UNICEF, Ministry of Health and Uganda Paediatric Association member and other international bodies that support maternal and child health)
- ≥ 18 years of age (providers, administrators) or ≥ 15 years of age (parents)

4.3.2 Exclusion criterion

- Participant does not provide written informed consent to take part in FGD/interview (Appendix B)

4.4 Withdrawal of Participants

A study participant will be discontinued from participation in the study if any situation occurs such that continued participation in the study would not be in the best interest of the participant (see Section 9 for additional details). Participants are free to withdraw from the study at any time without giving a reason.

5. Study Procedures

All study procedures will be conducted in accordance with ICH-GCP principles and all research personnel involved in the study will undergo ICH-GCP training. Healthcare workers at the study sites will be trained on study objectives, overview of procedures, standardised management protocol and asked to inform study personnel of any potential participants and in the event of a clinical deterioration.

5.1 Internal Pilot

All study personnel will undergo training according to study specific procedures to ensure high quality recruitment, data collection, and intervention implementation (see Section 5.9). This will take place prior

to an internal pilot phase involving recruitment of 10 participants at each site; piloting of data collection tools and processes; and provision of the intervention alongside other medical therapies (e.g., oxygen, IV fluids). This will enable refinement of the study procedures and documentation. Initially, the internal pilot will take place at EH only. Once study personnel at EH demonstrate successful performance of trial procedures, the internal pilot phase will commence at the four remaining hospital sites (IH, JH, MH, KNRH). If procedures are judged to be adequate and in accordance with ICH-GCP principles, internal pilot participants will be included in the sample for the overall trial.

5.2 Screening

[figure not shown]
All new admissions to the newborn units at JH, IH, EH, KNRH and MH will be screened for eligibility by trained study staff. Eligibility will be assessed as soon as possible after admission and once the baby is aged 1h or older. This is in recognition of the large physiological changes that take place following delivery and that the stability of a newborn aged <1h may change rapidly and not accurately reflect the stability over the following 24h. All screening procedures will be performed by study nurses or medical research officers, with support from the study paediatrician at each site. Oral informed consent will be obtained from a parent/caregiver prior to the initiation of screening procedures.

Screening procedures will take place at the radiant heater or incubator where the neonate has been admitted in the following order:

1. Neonatal chronological age will be ascertained by questioning the parent/caregiver and/or examining the antenatal card, medical record, or referral notes.
2. Weight will be measured using the study scale (Seca) to ensure weight is $\geq 700\text{g}$ and $\leq 2000\text{g}$.
3. A focused physical examination will be conducted to assess for the presence of visually recognisable major congenital malformations, severe jaundice, and seizures.
4. A pulse oximeter with neonatal probe will be attached for continuous monitoring and documentation of HR and SpO₂ for an initial 10 minutes.

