10.1 Sample Size

Surveillance data collected on admissions to the JH neonatal unit between January and December 2016 (Perinatal Audit Data from Uganda Paediatric Association) suggest that the mortality rate in the control arm will be at least 25% across the four sites. The most recent Cochrane review and a metaanalysis demonstrated large mortality reductions among stable neonates (RR 0.60 and 0.64 respectively) (2,3), and the RCT in Ethiopia published a RR for mortality amongst neonates before stabilisation of 0.57 (4). Assuming a conservative control mortality rate of 25% across the 4 hospitals in our study, 1750 neonates (875 per arm) would enable us to detect a relative difference between arms of 22.4% (5.6% absolute difference) with 80% power and a significance level of 5%. If the control mortality rate were in fact as low as 18%, we would still be able to detect a relative difference of 27% (absolute difference of 4.8%). We plan to recruit 2188 neonates (1094 per arm) in order to allow for 10% withdrawal due to clinical deteriorations and consent withdrawal, and 10% dilution due to

noncompliance and loss to follow-up. This sample size would enable us to detect absolute reductions of 6.3% and 5.4% from control rates of 25% and 18%, respectively, with 90% power. Results from the feasibility study suggest that ≥ 400 eligible neonates are admitted to JH per year. Preliminary data suggest ~ 500 eligible neonates each are admitted to IH and EH per year and ~ 800 eligible neonates are admitted to MH per year. Recruitment will take place over 24 months, leading to an eligible population of ~ 4400 neonates. Thus, we have applied a conservative recruitment rate of $\sim 50\%$ to achieve the target sample of 2188. The admissions audit data from our feasibility study suggest that a higher recruitment rate should be achievable. Recruitment will continue until the target sample is reached, up to a maximum of 27 months, which includes a 3-month buffer period in case recruitment is delayed or slower than expected.

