10.2.2 Primary and secondary outcome analyses

The primary and secondary outcome analyses will be carried out on all neonates as randomised ('intention to treat'). Analysis will follow a pre-specified analysis plan approved by the TSC and DSMB prior to unblinding the study database. The criterion for statistical significance at the final analysis will be $P < 0.05$. The rate of loss to follow up will be reported. We will report risk ratios for mortality seven days after enrolment (primary outcome) and 28 days after enrolment (secondary outcome) for intervention versus control with associated 95% confidence intervals. Secondary outcomes: time from intervention/control procedures starting to death and length of hospital stay, will be analysed using Kaplan-Meier plots and the hazard ratios with accompanying 95% CI calculated using Cox proportional hazards regression. All other secondary outcomes will be analysed using appropriate regression models accounting for the nature of the distribution of the outcome and results will be presented as appropriate effect sizes with a measure of precision (95% confidence intervals). Both unadjusted analyses and analyses adjusted for stratification factors will be carried out. Additional exploratory analyses will control for any baseline measures that appear to be imbalanced between arms.

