10.2.3 Subgroup and adjusted analyses

Subgroup analyses are planned to explore between-group difference in the impact of KMC compared to standard of care on mortality, by GA (<28, 28-32, or >32 weeks), birthweight (<1000, 1000-1499, or ≥ 1500 g), hospital site, and level of predicted mortality risk based on the NMR-2000 score [high (≤ 16), medium (17-22), low (≥ 23)]. A paediatrician or medical research officer will conduct a Ballard examination to determine GA (27). GA is an important predictor of newborn survival. In settings with specialised neonatal care without intensive care, such as the five recruitment sites, neonatal mortality rates are 86% in neonates born at <28 weeks and 41% in neonates born at 28 to 31 weeks (51). The NMR-2000 is a simplified score to predict in-hospital mortality among neonates ≤ 2000 g, which has been validated in the UK and The Gambia (69). NMR-2000 uses data on three parameters (birthweight, SpO₂ at admission, highest level of respiratory support at any point within 24 hours of birth), which are already being collected on enrolled neonates.

Further exploratory analyses will be carried out to explore the association between mortality and time of initiation (<12, 12-<24, or ≥24 hours), and continuity of KMC (median hours per day: <6, 6-<12, 12-<18, or 18-24 hours).

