participants when they return for follow-up. Peer counselling will address many maternal concerns and may help facilitate longer durations of KMC. A related RCT demonstrated the efficacy of peer counselling in promoting breastfeeding amongst hospitalised neonates (97). We will also engage hospital administrators about KMC guidelines. Adjustable beds and KMC wraps will be provided, as these have been shown to improve adherence (98). Increased space is being organised for the JH and MH newborn units for KMC beds/chairs and existing incubators.

18. Significance of the Proposed Work

Globally, there are an estimated 2.5 million neonatal deaths each year (15), among which >80% occur in neonates who are small at birth, due to being preterm and/or SGA (16). Major mortality reductions could be achieved by improving care of small neonates in low-resource settings (16–18). WHO guidelines recommend KMC for “routine care of newborns weighing $\leq 2000\text{g}$... initiated as soon as newborns are clinically stable” (8), where stability has been defined as vital functions (breathing, circulation) not requiring “continuous medical support and monitoring,” and not being “subject to rapid and unexpected deterioration” (3). However, estimates suggest that $\geq 75\%$ of neonatal deaths occur before stabilisation in settings without intensive care (16,17,22). Further, over three-quarters of neonates in sub-Saharan Africa and south Asia lack access to intensive care (99). The only RCT of KMC in neonates before stabilisation with mortality outcomes was conducted in Ethiopia (123 neonates $\leq 2000\text{g}$). It reported a 43% reduction in mortality (RR 0.57); yet, 66% of deaths and the major difference between arms occurred within 12 hours of birth (18,23). In addition, this RCT excluded $>50\%$ of eligible neonates, did not utilise allocation concealment, and had an apparent group imbalance at baseline (favouring KMC) (23), compromising robustness (18,100). Thus, the effect of KMC initiated before stabilisation in hospitals without neonatal intensive care remains a research priority, still not being addressed, and a well-designed RCT is warranted to examine mortality impact in non-intensive care settings (18).

19. Publication and Dissemination Plan

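### Section 10.2.2 admits prognostic baseline measures other than birthweight band and site only through exploratory models chosen by observed imbalance, so a modest precision gain on mortality from data already collected is missed

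*Protocol*

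**What the plan says.** **Measures available before allocation**
- SpO₂ and heart rate: section 5.2 states "A pulse oximeter with neonatal probe will be attached for continuous monitoring and documentation of HR and SpO₂ for an initial 10 minutes".
- Age: ascertained as the first screening step (5.2). Section 4.2.1 admits "Chronological age 1-48 hours at time of screening". Date and time of birth are also baseline items (5.5.2).
- Respiratory support: this is not in the 5.2 list. Oxygen and CPAP are among the therapies that define eligibility (4.2.1), and interventions since birth are baseline items (5.5.2).
- Timing: allocation is shown only once the required screening data have been entered (3.2.1), and randomisation follows the necessary baseline data (5.6).

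**Prognostic value**
- Section 10.2.3: "The NMR-2000 is a simplified score to predict in-hospital mortality among neonates". Its three parameters are birthweight, SpO₂ at admission and the highest respiratory support within 24 hours of birth. It is used there only to define subgroups.
- Section 18, on the earlier Ethiopian trial before stabilisation: "66% of deaths and the major difference between arms occurred within 12 hours of birth".

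**Analysis rule**
- Section 10.2.2: "Both unadjusted analyses and analyses adjusted for stratification factors will be carried out". The stratification factors are birthweight in three bands and site (3.2.1).
- The same section reserves control for other baseline measures to exploratory analyses of those that look imbalanced between arms. It names neither the unadjusted nor the stratum-adjusted result as the main one.

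**The concern.** Adjusting for a baseline covariate gains precision because the covariate predicts the outcome, not because it happens to differ between arms. Section 10.2.2 uses the second criterion for everything except birthweight band and site. It applies that criterion after the data are seen and calls the result exploratory. A strong predictor of death that is well balanced is never used. One that is imbalanced is used only in a model that cannot serve as the main result. Neither route improves the primary comparison.

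At stake is the width of the interval for 7-day and 28-day mortality in a trial of about 2188 small neonates. Adding participants is the expensive way to narrow that interval. The data for the cheap way are already being gathered.

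**Working it through.** **1. Reproduce the protocol's figure (10.1).** The protocol states "Assuming a conservative control mortality rate of 25% across the 4 hospitals in our study" and "1750 neonates (875 per arm) would enable us to detect a relative difference between arms of 22.4% (5.6% absolute difference) with 80% power".
- Two proportions, pooled variance, two-sided 5%, no continuity correction: 25% v 19.4% needs 864 per arm for 80% power, against 875 stated. Power at 875 per arm is 80.5%.
- Low-rate case, 18% v 13.2%: power at 875 per arm is 79.1%. With exactly a 27% reduction (18% v 13.14%), 873 per arm suffices.
- Inflation: 1750 / 0.80 = 2188.

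The figures reproduce as an unadjusted comparison. The stated power does not depend on any covariate.

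**2. Variance of the risk difference, n = 1750, 1:1.**
- Unadjusted: V = 2[p₀(1−p₀) + p₁(1−p₁)] = 2[0.25×0.75 + 0.194×0.806] = 0.6877.
- Standardised over covariates X: V = 2E[p₀(X)(1−p₀(X))] + 2E[p₁(X)(1−p₁(X))] + Var[p₁(X)−p₀(X)].
- Power = Φ(0.056/√(V/1750) − 1.96).

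Unadjusted: √(0.6877/1750) = 0.01982; 0.056/0.01982 = 2.825; power 80.6%.

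**3. Add birthweight bands, which 10.2.2 already plans.** Band shares come from Table 1: 29/254, (110−29)/254 and 144/254, or 11%, 32% and 57%. Control risks by band are not in the protocol. The assumed ranges are 50–70%, 32–36% and 10–16%, averaging 25%.

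Worked case: control risks 50%, 32%, 16%, with a common odds ratio giving 41.4%, 24.9%, 11.9% (average 19.4%).
- E[p₀(1−p₀)] = 0.114×0.250 + 0.319×0.218 + 0.567×0.134 = 0.174
- E[p₁(1−p₁)] = 0.114×0.243 + 0.319×0.187 + 0.567×0.105 = 0.147
- Var[p₁−p₀] is about 0.0003
- V = 2×0.174 + 2×0.147 + 0.0003 ≈ 0.642; power 83%

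Across the assumed band risks, power is 83 to 89%.

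**4. Add a pre-allocation severity index.** A standard normal index stands in for SpO₂, respiratory support and age together. Its log odds ratio per SD is assumed to be 0.4 to 1.0.

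| | Weak (0.4) | Strong (1.0) |
|---|---|---|
| Variance relative to bands only, across band risks | about 0.974 | down to 0.862 |
| Equivalent extra babies, 1750×(1/ratio − 1) | 47 | 280 |
| Worked case: power with bands, then with index | 83% to 84% | 83% to 88% |

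Across all settings, power with bands plus index is 84 to 93%. Within any one set of band risks, the step beyond bands is about 1 to 5 points.

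**5. Two cross-checks.**
- Power at n/(1−R²), with assumed extra explained variance of 2%, 5%, 10% and 15%: 80.5% becomes 81.3%, 82.5%, 84.5% and 86.4%.
- Simulation of standardised risk ratios (2000 trials per setting), strata-adjusted then with the index: 84.6% to 85.2% (log odds ratio 0.4), 84.8% to 87.4% (0.7), 82.6% to 89.1% (1.0). The gain is about 1 to 7 points.

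Twin pairing is ignored throughout.

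**The case against.** **The covariate list belongs in the analysis plan.** Section 10.2.2 refers to a pre-specified plan that is not shown here, and that plan may name more covariates. This would dispose of the point if the protocol were silent. It is not: it states a rule for other baseline measures, and selection by imbalance is a poor one. If the plan already lists prognostic covariates, 10.2.2 should be brought into line with it.

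**Stratum adjustment is valid and standard.** This stands. A reader might infer that 10.2.2 limits adjustment to the stratification factors alone. It does not say so: it also plans unadjusted and exploratory analyses.

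**The gain is assumed.** This stands. The protocol gives no prognostic strength. The strong end may be optimistic, because severely unstable babies are excluded (4.2.2). CPAP is given only where it is local standard of care (3.2.6), so respiratory support partly overlaps with site. The rise from 80.6% to as much as 93% must not be credited to the new covariates, since part of it comes from the birthweight bands already planned.

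**Time at risk.** A reader might infer that a baby entering at 48 hours has about two days less at risk. That holds only if the window runs from birth (Definitions, day 0–6). Section 10.2.2 counts seven days from enrolment, which gives every baby the same window. What survives on either reading is that older entrants have already lived through the early hours.

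**Chance imbalance is not bias.** This is correct. Randomisation and the interval allow for it, and the loss is one of precision.

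**Conclusion.** The point holds as a missed precision gain. Predictors that the protocol itself recognises are available before allocation, yet they can reach the mortality analysis only through an exploratory, imbalance-driven step.

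The size is modest: a further 3 to 14% off the variance and about 1 to 5 points of power beyond strata adjustment (about 1 to 7 by simulation). This rests on the assumed log odds ratio of 0.4 to 1.0 per SD and the assumed band risks. At the weak end it is negligible.

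A reader might infer that the trial is underpowered or its sample size wrong. The documents do not support that, because 80% power at 25% v 19.4% is met unadjusted. Nor is every item shown to be recorded in the section 5.2 screening list: respiratory support comes from 4.2.1 and 5.5.2. The change is worth making because it costs almost nothing, not because a stated claim fails.

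**What to change.** In section 10.2.2:
- Pre-specify that the adjusted model for 7-day and 28-day mortality includes site, birthweight, SpO₂ at screening, respiratory support at screening (none, oxygen, CPAP) and age at randomisation in hours.
- Use only values recorded before allocation. The respiratory-support item of NMR-2000 covers the first 24 hours of life and can fall after randomisation, so it must not be the covariate.
- Report a standardised (marginal) risk ratio from the logistic model with robust standard errors. This keeps the planned effect measure.
- Delete covariate selection by observed imbalance.
- Reconcile the outcome window, from birth (Definitions) or from enrolment (10.2.2), because it determines what age at randomisation represents.

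Settle the wording before unblinding. The cost is a few more model terms, set against roughly 390 expected deaths (875×0.25 + 875×0.194 = 388.5), and separate coding of the pre-allocation respiratory-support value. No new measurement or visit is needed.
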